17.1 Extent of Exposure

For the expansion part, the number of doses received, the duration of exposure to enapotamab vedotin (days), the actual cumulative dose (mg), as well as the actual and relative dose intensities (continuous and in categories: >= 110%, 90% to < 110%, 70% to < 90%, 50% to < 70%, < 50%, missing) will be summarized by means of descriptive statistics using the safety set.

Version: 4.0

The duration of exposure to enapotamab vedotin (days) will also be presented by a Kaplan-Meier plot (without censoring).

Also, the number of subject days (total number of days in trial) will be presented by means of descriptive statistics for each dose/cohort group.

For the dose-escalation part, only the number of doses received, number of days in the trial and the duration of exposure will be presented as mentioned above.

17.2 Adverse Events

Summary tables for AEs described below will include only AEs that are treatmentemergent, i.e. AEs that started or worsened (taking into account the dates of grade changes) during the treatment period including the safety follow-up period.

Adverse events collected during the pre-treatment will be tabulated together with the medical history (by SOC and PT) and will be included in the serious AE listing (marked with a flag). Adverse events collected during the follow-up period will be tabulated separately from the treatment-emergent AEs and will be included in the AE listings (marked with a flag).

See section 4.1.1 for definition of pre-treatment, treatment and follow-up periods.

Missing or partial AE start date will be estimated in order to include events in summary tables in case of doubt (see section 4.7 for more details).

A summary table will present the number and percentage of subjects with at least one:

- Treatment-emergent adverse event (TEAE)
- TEAE related to enapotamab vedotin
- Infusion-related TEAE
- TEAE leading to permanent discontinuation of the trial treatment
- TEAE leading to drug interruption
- TEAE leading to dose reduction
- Serious TEAE
- Serious TEAE related to enapotamab vedotin
- Grade ≥3 serious TEAE
- Grade ≥3 serious TEAE related to enapotamab vedotin
- Fatal TEAE
- Fatal TEAE related to enapotamab vedotin

TPL N°: eTPL SA-02-01 TPL Version: 02

Of SOP SA-02.08
TPL Effective Date: 31 Mar 2016
Approved in Vault: 6/30/2021

- Grade ≥3 TEAE
- Grade ≥3 TEAE related to enapotamab vedotin
- Grade ≥3 TEAE leading to permanent discontinuation of the trial treatment
- TEAE of special interest (AESI): constipation, neutropenia, peripheral neuropathy, vomiting, diarrhea, hyponatremia and possibly other types of adverse events¹
- TEAE of special interest (AESI) leading to permanent discontinuation of the trial treatment: constipation, neutropenia, peripheral neuropathy, vomiting, diarrhea, hyponatremia and possibly other types of adverse events²
- Grade 1 TEAE of special interest by type
- Grade 2 TEAE of special interest by type
- Grade 3 TEAE of special interest by type
- Grade 4 TEAE of special interest by type
- Grade 5 (fatal) TEAE of special interest by type
- Medication errors and overdose TEAEs

The AE summary table will also be repeated for all subjects on 2.2 mg/kg across escalation and expansion, all subjects on 1.0 mg/kg across escalation and expansion, and all patients across escalation and expansion (i.e. three columns).

The following tabulations will be presented by PT (order by decreasing frequency), by SOC and PT (order by decreasing frequency of SOC and by decreasing frequency of PT within SOC) and by SOC or type, PT and highest NCI-CTCAE grade (order by decreasing frequency of SOC or type and by decreasing frequency of PT within SOC) as indicated:

- All TEAEs by PT
- Most frequent (20%) TEAEs by PT
- All TEAEs by SOC and PT
- All AEs during the follow-up period by SOC and PT and highest NCI-CTCAE grade
- All TEAEs by SOC and PT and highest NCI-CTCAE grade²
- TEAEs related to enapotamab vedotin by PT
- TEAEs related to enapotamab vedotin by SOC and PT
- TEAEs related to enapotamab vedotin by SOC and PT and highest NCI-CTCAE grade³
- NCI-CTCAE grade ≥3 TEAEs by PT
- Most frequent (5%) NCI-CTCAE grade ≥3 TEAEs by PT

Page 30 of 46

TPL N°: eTPL SA-02-01 Of SOP SA-02.08 TPL Effective Date: 31 Mar 2016

¹ AEs of special interest will be tabulated by AESI type. The AESI types will be defined using MedDRA SMQ lists or preferred term lists provided by sponsor at the time of the analysis programming.

² AEs of special interest will be tabulated by AESI type. The AESI types will be defined using MedDRA SMQ lists or preferred term lists provided by sponsor at the time of the analysis programming.

³ Only most frequent AEs (> X% of Any Grade overall) will be included. The X% will be defined at the time of the analysis programming.

Version: 4.0

- NCI-CTCAE grade ≥3 TEAEs related to enapotamab vedotin by PT
- NCI-CTCAE grade ≥3 TEAEs by SOC and PT
- TEAEs leading to permanent discontinuation of the trial treatment by PT
- TEAEs leading to drug interruption by PT
- TEAEs leading to dose reduction by PT
- TEAEs of special interest by type and PT
- TEAEs of special interest by type and PT and highest NCI-CTCAE grade
- TEAEs of special interest related to enapotamab vedotin by type and PT
- NCI-CTCAE grade ≥3 TEAEs of special interest by type and PT
- Serious TEAEs of special interest by type and PT
- TEAEs of special interest leading to permanent discontinuation of the trial treatment by type and PT

In all tabulations, subjects will only be counted once for each preferred term. In case a subject experienced the same event more than once or has reported grade changes, the highest NCI-CTCAE grade will be presented.

In addition, time to onset of first AESI (for subjects with at least one event), total number of AESI events, total number and percentage of AESI events with outcome of resolution, and time to resolution of each AESI event (for events which are resolved) will be summarized by AESI type using descriptive statistics. AESI events with partial start date will be imputed accordingly to the rules described in section 4.7.

Time to onset of first AESI event will also be presented graphically by AESI type using a cumulative distribution function (one plot with one line for each AESI type); subjects with no AESI will not be included. This plot will also be presented for all subjects on 2.2 mg/kg across escalation and expansion and one for all subjects on 1.0 mg/kg across escalation and expansion.

For subjects with constipation, the number of subjects who did or didn't use prophylactic laxatives (based on diary data) will be tabulated.

For subjects with neutropenia, the number of subjects who did or didn't use G-CSF (based on concomitant medications) will be tabulated.

Treatment-emergent adverse events of special interest will also be presented in a table by type, cycle and preferred term and in a segmented bar-chart (each segment displays highest NCI-CTCAE grade with % of subjects who experience AESIs and related AESIs over time. Note: the % over time should be based on subjects still in the trial at the time of the corresponding cycle. When the same adverse event occurs more than once, only the first event will be included (similarity is defined based on the preferred term). Adverse events will be assigned to the cycle based on the onset date of this first AE. The highest NCI-CTCAE grade will take into account all occurrences of the same preferred term and all the individual grade changes as reported in the eCRF. The segmented bar-chart will also be produced for all subjects on 2.2 mg/kg across escalation and expansion and one for all subjects on 1.0 mg/kg across escalation and expansion.

Listings of all treatment-emergent adverse events will be provided including the subject identifier (including site and country), age, race, sex, verbatim, preferred term, duration of the event, highest NCI-CTCAE grade, reported NCI-CTCAE grade, grade changes and timing of grade changes, action taken, outcome, causality, date of onset, cycle of onset, date of resolution, days since the first dose, days since the last dose, serious (Y/N), DLT

Page 31 of 46

TPL N°: eTPL SA-02-01 Of SOP SA-02.08 TPL Effective Date: 31 Mar 2016

(Y/N) for dose-escalation part, adverse event of special interest (Y/N) and infusion reaction (Y/N).

In addition, the most frequent adverse events will be presented in a segmented bar-chart for all subjects on 2.2 mg/kg across escalation and expansion and one for all subjects on 1.0 mg/kg across escalation and expansion.

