In order to obtain sufficient evaluable fresh tumor biopsies, up to 15 additional subjects may be recruited in Cohort 6 to ensure that 25 fresh biopsies are acquired. A maximum of 45 subjects may therefore be enrolled in Cohort 6. A higher number of biopsies are required in this cohort due to the mixture of tumor types being enrolled.

Cohort 8 will further explore the safety and efficacy of the 1.0 mg/kg 3Q4W schedule in NSCLC subjects without EGFR/ALK mutations. This is the same subject population as Cohort 2 where a preliminary efficacy signal was observed for the 1Q3W schedule. Cohort 8 will include up to 37 subjects with the aim to collect evaluable fresh tumor biopsies from 15 subjects. Recruitment is not linked to the number of biopsies collected and may continue up to a maximum of 37 subjects even if 15 fresh tumor biopsies have already been obtained. The benefit/risk balance will be evaluated on an ongoing basis in this cohort.

More details can be found in section 10.9 Sample Size Estimation of the protocol final version 10.0, dd. 9 December 2019.

4. General Analysis Definitions

Data will be analyzed using SAS (Version 9.4 or higher). For graphs R (Version 3.3.2 or higher) can be used in addition.

Descriptive statistics will be tabulated as follows:

- Categorical data will be summarized in contingency tables presenting frequencies and percentages.
- Continuous data will be summarized using number of non-missing values (n), mean, standard deviation, median, 25th and 75th percentiles, minimum and maximum values.
- Time to event parameters will be described using Kaplan-Meier estimates: median time, first and third quartiles along with approximate 95% confidence intervals (the default conftype=loglog in proc lifetest will be used). The 3, 6, 9 and 12 months event-free rates will also be presented together with the 95% confidence intervals.

Page 8 of 46

TPL N°: eTPL SA-02-01 Of SOP SA-02.08 TPL Effective Date: 31 Mar 2016 TPL Version: 02

The results will be presented by 1Q3W and 3Q4W dose-escalation and expansion parts separately. Results will be presented for both trial parts unless specified otherwise.

The results will be presented by groups and total. In the dose-escalation 1Q3W and 3Q4W arms of the trial, groups are defined by dose levels. In the expansion part, groups are defined by cohort, dose level and dosing regimen.

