15.1.5 Time to Confirmed Response according to RECIST 1.1 - Expansion

Time to Confirmed Response (TOR) is defined as the number of weeks from date of first IMP administration to the date of first response (CR or PR) according to RECIST 1.1. Only responders will be included in the analyses (no censoring). TOR will be analyzed using the

Page 25 of 46 TPL N°: eTPL SA-02-01

TPL Effective Date: 31 Mar 2016 Approved in Vault: 6/30/2021

Of SOP SA-02.08

same statistical methodology as PFS. For these analyses, only confirmed responses will be used. Both the response assessments from the investigator will be presented.

Version: 4.0

The time to event graph of TOR will represent only confirmed responders and will start from the bottom-left corner (no responders) to the top-right corner.

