2.1 Planned Analyses

Data collected up to and including the data cut-off date of 22 March 2021 has been reported in the CSR as per SAP version 4 dd. 30 June 2021. Data collected after the 22 March 2021 data cut-off date until the end of trial (last patient end of safety follow-up on 12 November 2021) will be reported in an addendum to the CSR based on the reporting described in this SAP addendum. This reporting in the addendum to the CSR includes data from the 3 subjects who remained on treatment after 22 March 2021 as well as data from the 47 subjects who remained in the (survival) follow-up period after 22 March 2021.

Populations will be defined as described in the SAP version 4 dd. 30 June 2021. Programs from the main analyses will be reused with the same definitions and decision rules except for the definition of what constitute an AESI in the CSR Addendum.

Following outputs will be repeated from the main analyses:

- Subject disposition
- Progression free survival
- Overall survival
- TEAE by PT
- Drug-induced liver injury
- All listings of all data after the cut-off date of 22 March 2021

The following output will be added

- Time to onset of first TEAE (AESI only),
- Time to resolution (AESI only); with percentage of events with outcome of resolution
- Time to improvement of TEAE (AESI only), percentage of events with improvement; with percentage of events with improvement
- AE summary table (same categories as in the main CSR but with the AESI categories as described below and AESI leading to permanent discontinuation of the trial treatment added)
- TEAE by PT and maximum grade
- TEAE of special interest by AESI type and PT

Page 3 of 8

TPL N°: eTPL SA-02-01 Of SOP SA-02.08 TPL Effective Date: 31 Mar 2016

- TEAE of special interest by AESI type, PT and highest NCI-CTCAE Grade
- Enapotamab Vedotin Related TEAEs of Special Interest by AESI Type and PT
- NCI-CTCAE grade >= 3 TEAEs of Special Interest by AESI Type and PT
- Serious TEAEs of Special Interest by AESI Type and PT
- TEAEs of Special Interest Leading to Permanent Discontinuation of Trial Treatment
 by AESI Type and PT

The definition of AESI in the CSR Addendum:

- PN: AEs with PTs within the peripheral neuropathy MedDRA SMQ: Peripheral neuropathy SMQ [20000034] (Broad)
- Constipation: PT
- Neutropenia: PTs neutropenia, neutrophil count decreased and febrile neutropenia.

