Note: As "Immune related Adverse Events", which is generally associated with immune checkpoint inhibitors, didn't result in clinically significant findings in this study, its relevance is not applicable thus will not be included in the above AESI table.

All derived dataset programs will rerun on the whole database and contain all data. A flag marking new records and changed records will be added to each derived dataset.

3. Additional outputs

All available data from the start of the trial until the end of the trial will be included in the selected tables and graphs for all patients in the study.

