3.5 Time to resolution of AESI

Time to resolution (AESI only); with percentage of events with outcome of resolution will be summarized by AESI type using descriptive statistics. AESI events with partial start date will be imputed accordingly to the rules described in section 4.7 in the SAP version 4 dd. 30 June 2021.

Time to resolution is presented by AESI type for the three searches specified in section 2.1.

TPL N°: eTPL SA-02-01 TPL Version: 02

Of SOP SA-02.08 TPL Effective Date: 31 Mar 2016

Approved in Vault: 22 Feb 2022

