3.6 Time to improvement of AESI

Improvement is defined as a change in severity to a lower grade.

Total number and percentage of AESI events with improvement and time to improvement of each AESI event (for events which are improved) will be summarized by AESI type using descriptive statistics. AESI events with partial start date will be imputed accordingly to the rules described in section 4.7 in the SAP version 4 dd. 30 June 2021.

Time to improvement is presented by AESI type for the three searches specified in section 2.1.

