4.1 List of Statistical Tables and Graphs

General	Template*
Table A.14.01.01: Subject Treatment Disposition	Template 3
Table A.14.01.02: Subject Study Disposition	Template 4
Efficacy Evaluation	
Table A 14.02.01: PFS	Template 18
Graph A.14.02.02: PFS – Kaplan-Meier Curves	Template 41
Table A.14.02.03: Overall Survival	Template 18
Graph A.14.02.04: Overall Survival – Kaplan-Meier Curves	Template 41
Safety Evaluation	
Table A.14.03.01: Summary of Adverse Events	Template 24
Table A.14.03.02: Summary of Adverse Events – 1.0 mg/kg and 2.2 mg/kg arms	Template 24
Table A.14.03.03: TEAE by PT	Template 25
Table A.14.03.04: TEAE by PT and maximum grade	Template 27
Table A.14.03.05: TEAE of special interest – by AESI type and PT	Template 25
Table A.14.03.06: TEAE of special interest – by AESI type, PT and highest NCI-CTCAE Grade	Template 27
Table A.14.03.07: Enapotamab Vedotin Related TEAEs of Special Interest - by AESI Type	Template 25
and PT	
Table A.14.03.08: NCI-CTCAE grade >= 3 TEAEs of Special Interest - by AESI Type and PT	Template 25
Table A.14.03.09: Serious TEAEs of Special Interest - by AESI Type and PT	Template 25
Table A.14.03.10: TEAEs of Special Interest Leading to Permanent Discontinuation of	Template 25
Treatment - by AESI Type and PT	
Table A.14.03.11: Time to onset of First TEAE of Special Interest – by AESI Type	Template 28
Table A.14.03.12: Time to resolution of TEAE of Special Interest – by AESI Type	Template 28
Table A.14.03.13: Time to improvement of TEAE of Special Interest – by AESI Type	Template 28
Table A.14.03.14: Subject Incidence of Drug Induced Liver Laboratory Abnormalities	Template 35

^{*}Reference: SAP Mocks version 2, dd. 11February 2020

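### AESI times to resolution and improvement leave out events still open, so they run short by an amount that cannot be derived; separately, the 1.0 mg/kg safety pool names no schedule

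*SAP*

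**What the plan says.** **Resolution, main analysis.** SAP 17.2 plans the total number of AESI events, the number and percentage resolved, and then "time to resolution of each AESI event (for events which are resolved) will be summarized by AESI type using descriptive statistics". It gives no censoring rule for events without resolution.

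**Improvement, addendum.** SAP Addendum 3.6 defines improvement as a move to a lower grade and summarises "time to improvement of each AESI event (for events which are improved"), with the number and percentage improved.

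**Resolution, addendum.** Addendum 3.5 describes time to resolution "with percentage of events with outcome of resolution will be summarized by AESI type using descriptive statistics". It does not repeat the restriction to resolved events, but Addendum 2.1 says "Programs from the main analyses will be reused with the same definitions and decision rules", apart from a new AESI definition. That definition has three types: peripheral neuropathy, constipation and neutropenia. Addendum section 3 adds that "All available data from the start of the trial until the end of the trial will be included in the selected tables" and graphs.

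**General convention.** SAP section 4 states: "Time to event parameters will be described using Kaplan-Meier estimates: median time, first and third quartiles along with approximate 95% confidence intervals". The SAP departs from this openly elsewhere. For time to confirmed response, section 15.1.5 says "Only responders will be included in the analyses (no censoring"), and the exposure plot in section 17.1 is also uncensored.

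**The 1.0 mg/kg pool.** SAP 17.2 and Addendum 3.3 repeat some safety outputs for everyone dosed at 1.0 mg/kg in either trial part. No schedule is given. SAP 4.5.1 lists 1.0 mg/kg as a level in both the 1Q3W and the 3Q4W escalation. In the expansion (SAP 4.5.2) it is used only on 3Q4W, in Cohorts 6 and 8.

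**The concern.** A duration summarised only over events that ended while someone was watching is truncated. Short events get in; events that outlast observation do not. The median therefore describes the events that finished, not how long the toxicity lasts. The distortion is largest for slow events with little observation left after onset. It is smallest for events that start early in treatment or resolve quickly.

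The safety profile is part of the primary objective, and Protocol 9.1.9.3 wants neuropathy assessed in order to learn its clinical course. A reader who takes the tabulated median without its conditioning will think the toxicity shorter than it is. The SAP censors duration of response (15.1.6) but not duration of toxicity.

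The pool raises a smaller issue. A 1.0 mg/kg column will be read as the 3Q4W MTD group, yet its wording admits 1Q3W subjects, whose nominal weekly dose is much lower.

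**Working it through.** The plan states no figure for this point, so there is nothing to reproduce. The check has three parts.

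**1. What limits observation**

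- Non-serious AEs are reported up to the safety follow-up visit (Protocol 8.4.12), 30 days after the last treatment (5.6.5), with a window of +14 days (Table 11). This gives 30 to 44 days after the last dose.
- A dose delay beyond 12 weeks means withdrawal (Protocol 7.3.3, Dose Delays). On 1Q3W, a held dose could allow about 3 + 12 = 15 weeks from the last dose.
- An event that starts earlier is also observed for all remaining treatment.
- Before Amendment 10, suspected related AEs were collected at 12-weekly contacts until new anti-cancer treatment (Protocol 5.6.6).
- From Amendment 10, AEs are followed to resolution or the safety visit, with related serious events followed further (Protocol 17.6).
- The main report was cut at 22 March 2021 with three subjects still on treatment (Addendum 2.1).
- The text of Protocol 9.6, the follow-up rule before Amendment 10, is not in the public copy.

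**2. Illustration of the bias**

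Assume exponential resolution with true median m, observed for a time C after onset.

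- Proportion resolved: F(C) = 1 − 2^(−C/m).
- Resolved-only median t solves F(t) = F(C)/2, so t = −m · log2(1 − F(C)/2).

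For m = 16 weeks:

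| Observed after onset | Resolved | Resolved-only median (weeks) |
|---|---|---|
| 30 days | 17% | 2.0 |
| 44 days | 24% | 2.9 |
| 12 weeks | 41% | 5.2 |
| 15 weeks | 48% | 6.3 |
| 24 weeks + 44 days | 73% | 10.5 |

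Worked line for 15 weeks: F = 1 − 2^(−15/16) = 0.478, and t = −16 · log2(1 − 0.239) = 6.3. For the last row, C = 24 + 44/7 = 30.3 weeks.

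Fast events suffer little. With m = 2 weeks, the resolved-only median is 1.4 weeks at 30 days and 2.0 weeks at 12 weeks.

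Would censoring help if it were informative? A simulation of 400,000 events took m = 8 weeks, censoring uniform from 30 days to 15 weeks, and correlation between resolution and censoring times of −0.5, 0 and +0.5. The Kaplan-Meier median was 7.5, 8.0 and 8.4 weeks; the resolved-only median was 3.7, 3.7 and 3.8. Kaplan-Meier is not exact here, but it is much closer.

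**3. The pool**

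Nominal weekly dose at 1.0 mg/kg is 1.0/3 = 0.33 mg/kg on 1Q3W and 3 × 1.0/4 = 0.75 mg/kg on 3Q4W, a ratio of 2.25.

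Numbers treated are not given. Assumed ranges:

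- 1Q3W: 3 (the planned minimum in Protocol 5.2) to 9.
- 3Q4W escalation: 6 to 12 (six at the MTD, plus up to six more, Protocol 5.3).
- Expansion: 40 to 82, where 82 = 45 + 37 is the planned maximum of Cohorts 6 and 8.

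The 1Q3W share then runs from 3/(3 + 12 + 82) = 3/97 = 3% to 9/(9 + 6 + 40) = 9/55 = 16%.

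**The case against.** The case for leaving the plan alone has force. The SAP states the conditioning in words, prints the percentage resolved or improved beside the time, and lists outcome, resolution date and grade changes for each event. These are supplementary descriptive tables. A reader might infer that non-resolution is hidden; the documents do not support that. What remains is that neither the percentage nor the listing corrects the printed time.

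A reader might also infer that the SAP contradicts its own Kaplan-Meier convention. It does not: two other outputs omit censoring openly, so this is an unreconciled tension.

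The strongest objection concerns size. A reader might take 30 days to 15 weeks as the observation window for every event and conclude that reported medians cannot exceed half of it. Those periods run from the last dose, so they equal time from onset only for events starting about then. The half-window ceiling also belongs to the exponential: with a rising hazard (Weibull, shape 2), the long-duration limit is the window divided by 1.41. Collection of related AEs went on longer before Amendment 10, and the AESIs are largely described as treatment-related (Protocol 9.1.9). All of this stands, so no size can be claimed.

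Finally, inheritance by Addendum 3.5 is inferred: Addendum 2.1 lists time to resolution among added outputs, not repeated ones. The rule that programs are reused makes inheritance the natural reading, but 3.5 does not say it.

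**Conclusion.** The point holds and is minor. Time to resolution (SAP 17.2, and Addendum 3.5 by inference) and time to improvement (Addendum 3.6) are summarised only among events that reached that outcome. Open events are excluded rather than censored, so the times are biased short. That direction follows from the conditioning. The size does not follow from anything in the documents: they give no resolution times, and part of the follow-up text cannot be seen. The figures above rest on an assumed distribution and assumed onset times, and only show that the shortfall can range from trivial to large.

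The pool wording is a missing label. The paired MTDs in Protocol 3.3 (2.2 mg/kg for 1Q3W, 1.0 mg/kg for 3Q4W) suggest that a 3Q4W group was meant. A reader might infer that the mixed pool also feeds the resolution and improvement tables; those are by AESI type and do not use it. The 3% to 16% share rests on assumed counts. The 2.2 mg/kg pool is not ambiguous, because that level is listed only for 1Q3W.

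**What to change.** **Addendum Tables A.14.03.12 ("Time to resolution of TEAE of Special Interest") and A.14.03.13.** Keep the percentages resolved and improved. For each of the three AESI types:

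- Add a Kaplan-Meier estimate, or a cumulative incidence with death as a competing event, censoring open events at the last AE assessment.
- Report proportions resolved or improved at fixed times, for example 4, 8 and 12 weeks, because some medians will not be reached.
- State which outcomes count as resolved, since Protocol 9.1.8 also records end dates for fatal and recovering outcomes.
- Use the first event per patient, or note that repeated events within a patient are correlated.
- Note that censoring may be informative.

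The addendum tables cover the whole trial, so they can carry the censored estimates for all subjects.

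**Main report.** Footnote the resolution times as being among resolved events only.

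**Pool.** Restrict and label the addendum column (Table A.14.03.02) as 1.0 mg/kg 3Q4W, and footnote the main outputs that use the pool.

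**Cost.** One extra estimate per AESI type in two tables, one relabelled and rerun table, and footnotes to delivered outputs. Onset, resolution and grade-change dates are already collected, so no new data are needed.
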